6.5.7 Appropriateness of safety measurements

The safety assessments have been selected based upon the safety profile of the drug as reported in the Investigator Brochure, are standard for this patient population and drug class.

6.6 Other assessments

[REDACTED]

- Anti-AMG antibody collection

[REDACTED]

The timing and frequency of these assessments are outlined in [Table 6-1](#), [Table 6-2](#), [Table 6-3](#) and [Table 6-4](#) and [Table 6-5](#).

6.6.1 Patient Reported Outcomes (PROs)

[figure not shown]
Patients will complete all Patient Reported Outcome (PRO) questionnaires using the provided eDiary platform. For those questionnaires that are completed in-clinic, during visits, completion should occur before any other assessments are performed.

[figure not shown]
All questionnaires will be completed in the language most familiar to the respondent, at the scheduled study visit prior to the patient seeing the investigator for any clinical assessment or evaluation.

Patients should be given sufficient space and time to complete all study PROs. If patients experience any difficulties with submission after they complete the PROs, the study staff should assist them with submitting their PRO responses. Attempts should be made to collect responses to all PROs for all patients, including from those who prematurely discontinue prior to the study evaluation completion visit, however, if patients refuse to complete PROs, this should be documented in study source records.

Site staff will review eDiary compliance with the patient at each applicable visit. Completed questionnaires will be reviewed and examined by the investigator, before the clinical examination, for responses that may indicate potential adverse events (AEs) or serious adverse events (SAEs), and the review should be documented in the patient's source document accordingly. If AEs or SAEs are confirmed, then the physician must record the events as per instructions given in [Section 7.1](#) and [Section 7.2](#) of the protocol.

[REDACTED]

[Redacted text block]

6.6.4 Pharmacokinetics

Not applicable.

[REDACTED]

6.6.6 AMG 334 Antibody testing

Blood samples for antibody testing are to be collected for the measurement of anti-AMG 334 binding antibodies. Samples testing positive for binding antibodies will also be tested for neutralizing antibodies and may be further characterized for quantity/titer, isotype, affinity, and presence of immune complexes. Additional blood samples may be obtained for further evaluation of anti-AMG 334 antibodies during the study.

Sites will not be notified of positive neutralizing antibody results to the investigational product for a patient prior to that patient's final scheduled study visit. The patients with a positive neutralizing antibody response will continue to be dosed during the course of study.

During the **COVID-19 pandemic** that limits or prevents on-site study visits, or if visits by site staff to a patient's home are not feasible, the collection of samples may be modified by Novartis and will be communicated to the Investigator.

[REDACTED]

7 Safety monitoring

During the **COVID-19 pandemic** that limits or prevents on-site study visits, regular phone or virtual calls will occur (at the time of every scheduled visit or more frequently if needed) for safety monitoring and discussion of the patient's health status until the patient can again visit the site.

7.1 Adverse events

An adverse event (AE) is any untoward medical occurrence (e.g., any unfavorable and unintended sign [including abnormal laboratory findings], symptom or disease) in a patient or clinical investigation patient from randomization (Visit 101) until the end of study visit. Any events occurring during the Screening and Baseline Epochs should be documented as medical history. An AE may or may not be temporally or causally associated with the use of a medicinal (investigational) product.

In addition, all reports of intentional misuse and abuse of the product are also considered an adverse event irrespective if a clinical event has occurred.

The occurrence of adverse events must be sought by non-directive questioning of the patient at each visit during the study. Adverse events also may be detected when they are volunteered by the patient during or between visits or through physical examination findings, laboratory test findings, or other assessments.

Abnormal laboratory values or test results constitute adverse events only if they fulfill at least one of the following criteria:

- they induce clinical signs or symptoms,
- they are considered clinically significant,
- they require therapy.

Clinically significant abnormal laboratory values or test results must be identified through a review of values outside of normal ranges/clinically notable ranges, significant changes from baseline or the previous visit, or values which are considered to be non-typical in patient with underlying disease. Investigators have the responsibility for managing the safety of individual patient and identifying adverse events. Alert ranges for laboratory and other test abnormalities are included in [Appendix 1](#).

Adverse events must be recorded in the Adverse Events eCRF under the signs, symptoms or diagnosis associated with them, accompanied by the following information:

- the severity grade

- mild: usually transient in nature and generally not interfering with normal activities
- moderate: sufficiently discomforting to interfere with normal activities
- severe: prevents normal activities
- its relationship to the study treatment (no/yes)
- its duration (start and end dates) or if the event is ongoing an outcome of not recovered/not resolved must be reported
- whether it constitutes a serious adverse event (SAE - See [Section 7.2](#) for definition of SAE) and which seriousness criteria have been met
- action taken regarding [investigational] treatment.

All adverse events must be treated appropriately. Treatment may include one or more of the following:

- no action taken (e.g. further observation only)
- investigational treatment dosage increased/reduced
- investigational treatment interrupted/withdrawn
- concomitant medication or non-drug therapy given
- non-drug therapy given
- patient hospitalized/patient's hospitalization prolonged (see [Section 7.2](#) for definition of SAE)
- its outcome (not recovered/not resolved; recovered/resolved; recovering/resolving, recovered/resolved with sequelae; fatal; or unknown)

Once an adverse event is detected, it must be followed until its resolution or until it is judged to be permanent, and assessment must be made at each visit (or more frequently, if necessary) of any changes in severity, the suspected relationship to the study drug, the interventions required to treat it, and the outcome.

Information about common side effects already known about the investigational drug can be found in the Investigator Brochure (IB). This information will be included in the patient informed consent and should be discussed with the patient during the study as needed. Any new information regarding the safety profile of the medicinal product that is identified between IB updates will be communicated as appropriate, eg, via an Investigator Notification or an Aggregate Safety Finding. New information might require an update to the informed consent and has then to be discussed with the patient.

The investigator must also instruct each patient to report any new adverse event (beyond the protocol observation period) that the patient, or the patient's personal physician, believes might reasonably be related to study treatment. This information must be recorded in the investigator's source documents; however, if the AE meets the criteria of an SAE, it must be reported to Novartis.

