3.6 Risks and benefits

AMG 334 is being developed as for migraine prophylaxis in a large clinical development program including more than 4800 patients. Key risks and benefits are briefly summarized below. For further information, please refer to the most recent Investigator Brochure.

There were no significant findings in the toxicology studies with AMG 334 that would predict a risk to human patients. There were no significant effects on electrocardiogram (ECG) parameters, blood pressure (BP) or respiration rate in the single dose cardiovascular study in cynomolgus monkeys.

As of May 2019, approximately 4817 patients have received at least 1 dose of AMG 334, accounting for approximately 4418 patient-years. To date, no important risk has been identified for AMG 334.

A theoretical cardiovascular safety risk with CGRP pathway blockade is lack of compensatory vasodilation, particularly in the context of the coronary circulation during ischemic-related conditions although there has been no clinical evidence suggesting that selective blockade of the CGRP pathway during ischemia worsens myocardial ischemia to date. Patients in clinical trials will continue to be monitored for cardiovascular effects, and patients with pre-existing cardiovascular disease will be excluded from participation.

All biologicals, including fully human proteins, have the potential to induce immunogenicity leading to the development of specific anti-drug antibodies. So far, the development of anti-AMG 334 antibodies was not associated with specific adverse events or a clinically relevant reduction in AMG 334 plasma levels. Patients in clinical studies will continue to be monitored for the development of anti-AMG 334 antibodies and associated clinical sequelae.

Plasma levels of CGRP increase with advancement of pregnancy up to the time of delivery, followed by a sharp decline at term and postpartum in rats and humans. Endogenous CGRP may play an important role in maintaining normal fetoplacental development, fetal survival, and vascular adaptation during pregnancy. Women who are breastfeeding, pregnant, or planning to become pregnant are excluded from study participation, as well as patients who are unwilling to comply with the protocol-specified contraception requirements. All women of child bearing potential will be screened for pregnancy at each study visit.

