6.2 Patient demographics/other baseline characteristics

Patient demographic and baseline characteristic data will be collected on all patients include: date of birth, age, sex, race, ethnicity, source of patient referral, relevant medical history/current medical condition present before signing informed consent where possible, diagnoses and not symptoms will be recorded.

Prior headache characteristics and previous headache medication history, including information on the suitability for migraine prophylactics will be collected as part of baseline characteristics.

Investigators will have the discretion to record abnormal test findings on the medical history eCRF whenever in their judgment, the test abnormality occurred prior to the informed consent signature.

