7.2 Serious adverse events

7.2.1 Definition of SAE

An SAE is defined as any adverse event [appearance of (or worsening of any pre-existing)] undesirable sign(s), symptom(s) or medical condition(s) which meets any one of the following criteria:

- is fatal or life-threatening
- results in persistent or significant disability/incapacity
- constitutes a congenital anomaly/birth defect
- requires inpatient hospitalization or prolongation of existing hospitalization, unless hospitalization is for:
 - routine treatment or monitoring of the studied indication, not associated with any deterioration in condition (specify what this includes)
 - elective or pre-planned treatment for a pre-existing condition that is unrelated to the indication under study and has not worsened since signing the informed consent
 - treatment on an emergency outpatient basis for an event not fulfilling any of the definitions of a SAE given above and not resulting in hospital admission
 - social reasons and respite care in the absence of any deterioration in the patient's general condition
- is medically significant, e.g. defined as an event that jeopardizes the patient or may require medical or surgical intervention.

All malignant neoplasms will be assessed as serious under “medically significant” if other seriousness criteria are not met.

Life-threatening in the context of a SAE refers to a reaction in which the patient was at risk of death at the time of the reaction; it does not refer to a reaction that hypothetically might have caused death if it were more severe (please refer to Annex IV, ICH-E2D Guideline).

Medical and scientific judgment should be exercised in deciding whether other situations should be considered serious reactions, such as important medical events that might not be immediately life threatening or result in death or hospitalization but might jeopardize the patient or might require intervention to prevent one of the other outcomes listed above. Examples of such events are intensive treatment in an emergency room or at home for allergic bronchospasm, blood dyscrasias or convulsions that do not result in hospitalization or development of dependency or abuse (please refer to Annex IV, ICH-E2D Guideline).

Any suspected transmission via a medicinal product of an infectious agent is also considered a serious adverse reaction.

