7.2.2 SAE reporting

To ensure patient safety, every SAE, regardless of causality, occurring after the patient has provided informed consent and until the completion of the Follow-Up Epoch must be reported

to Novartis within 24 hours of learning of its occurrence. Any SAEs experienced after the completion of the Follow-Up Epoch should only be reported to Novartis if the investigator suspects a causal relationship to study treatment.

All follow-up information for the SAE including information on complications, progression of the initial SAE and recurrent episodes must be reported as follow-up to the original episode within 24 hours of the investigator receiving the follow-up information. An SAE occurring at a different time interval or otherwise considered completely unrelated to a previously reported one must be reported separately as a new event.

Information about all SAEs is collected and recorded on the Serious Adverse Event Report Form; all applicable sections of the form must be completed in order to provide a clinically thorough report. The investigator must assess the relationship of each SAE to study treatment, complete the SAE Report Form in English, and submit the completed form within 24 hours to Novartis. Detailed instructions regarding the submission process and requirements for signature are to be found in the investigator folder provided to each site.

Follow-up information is submitted as instructed in the investigator folder. Each re-occurrence, complication, or progression of the original event must be reported as a follow-up to that event regardless of when it occurs. The follow-up information should describe whether the event has resolved or continues, if and how it was treated, whether the blind was broken or not, and whether the patient continued or withdrew from study participation.

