7.5 Pregnancy reporting

To ensure patient safety, each pregnancy occurring after signing the informed consent must be reported to Novartis within 24 hours of learning of its occurrence. The pregnancy should be followed up to determine outcome, including spontaneous or voluntary termination, details of the birth, and the presence or absence of any birth defects, congenital abnormalities, or maternal and/or newborn complications.

Pregnancy must be recorded on the Pharmacovigilance Pregnancy Form and reported by the investigator to the local Novartis Drug Safety and Epidemiology Department. Pregnancy follow-up should be recorded on the same form and should include an assessment of the possible relationship to the study treatment.

Any SAE experienced during the pregnancy and unrelated to the pregnancy must be reported as an SAE.

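### Protocol 7.1 sends every pre-randomization event to medical history with no exception for serious ones, in conflict with 7.2.2, which requires SAEs to be reported from informed consent

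*Protocol*

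**What the plan says.** Protocol 7.1 defines an adverse event as an untoward occurrence "in a patient or clinical investigation patient from randomization (Visit 101) until the end of study visit". For the time before that it instructs: "Any events occurring during the Screening and Baseline Epochs should be documented as medical history". The sentence does not separate serious from non-serious events.

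Protocol 7.2.1 builds on the same term: "An SAE is defined as any adverse event" that meets one of a list of seriousness criteria.

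Protocol 7.2.2 sets a different starting point: "every SAE, regardless of causality, occurring after the patient has provided informed consent and until the completion of the Follow-Up Epoch must be reported" to the sponsor within 24 hours of the site learning of it.

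Four other places side with 7.2.2:
- Protocol 6.1 collects SAE data on patients who consented but never entered double-blind treatment.
- Table 6-1 marks the SAE row at the screening and baseline visits, while the AE row starts at Visit 101.
- Table 6-2 footnote 10 starts SAE collection at consent and non-serious AE collection at randomization.
- SAP 2.1.2 counts SAEs from consent to end of study and identifies them by the serious flag on the AE eCRF page.

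**The concern.** Section 7.1 is where a site would look to learn what counts as an adverse event and from when. Its instruction for Screening and Baseline is general and names a destination, the medical history record, that carries no reporting deadline. A site acting on it in good faith could enter a post-consent admission that meets a seriousness criterion as medical history and consider the matter closed.

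Two things would then be lost. The sponsor would not receive the 24-hour report that 7.2.2 requires. The event would also have no entry on the AE page, so the flag that SAP 2.1.2 relies on would not exist and the event would not be recognized as an SAE in the data. What is at stake is complete safety reporting before the first dose.

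**Working it through.** No figure in the plan is in dispute, so the main check sets the texts side by side.

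| Place | Start for serious events | Where they go |
|---|---|---|
| Protocol 7.1 | Randomization (Visit 101); no exception for serious events | Earlier events to medical history |
| Protocol 7.2.1 | None of its own; rests on the term adverse event | – |
| Protocol 7.2.2 | Informed consent | SAE Report Form, within 24 hours |
| Protocol 6.1 | After consent, for patients not entering double-blind treatment | SAE data collected |
| Protocol Table 6-1 | Visit 1 | SAE row marked |
| Protocol Table 6-2, footnote 10 | Informed consent | SAE collection |
| SAP 2.1.2 | Informed consent | Serious flag, AE eCRF page |

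**Step 1: is there a conflict?** Take an event after consent and before Visit 101 that meets a seriousness criterion. Under 7.1 it falls before the AE window and is directed to medical history. Since 7.2.1 defines an SAE as a kind of adverse event, a literal reader can conclude that it is not an SAE. Under 7.2.2 the same event must be reported within 24 hours. The two instructions differ for the same event.

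**Step 2: which passage is out of line?** Five places collect SAEs before randomization: 7.2.2, 6.1, Table 6-1, Table 6-2 footnote 10 and SAP 2.1.2. Only 7.1 points the other way. Table 6-1 and footnote 10 also show the evident intent, which is SAEs from consent and non-serious AEs from randomization. The 7.1 wording fits the non-serious half of that scheme only.

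**Step 3: would a misfiled event be picked up in the analysis?** Not through the SAP's own definition, because an event held only as medical history has no serious flag on the AE page. The SAE tables in SAP 2.7.1 are for the double-blind epoch, and SAP Table 4 starts that epoch after the first dose. The loss therefore concerns the record of SAEs from consent more than the comparison between arms.

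**Step 4: how much patient time is exposed?** The inputs are 246 randomized patients (protocol, Amendment 3 rationale), 4 weeks of Baseline plus 0 to 2 weeks of Screening, and 12 weeks of double-blind treatment (protocol 3.1).
- Lower end: 246 × 4 / 52 = 18.9 patient-years.
- Upper end: 246 × 6 / 52 = 28.4 patient-years.
- Double-blind epoch, for comparison: 246 × 12 / 52 = 56.8 patient-years.
- Ratio: 18.9 / 56.8 = 0.33 and 28.4 / 56.8 = 0.50.

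Screen failures add to this. SAP 1.1.2 planned for about 440 screened patients.

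**Step 5: how many events?** The documents give no pre-randomization SAE rate. For scale only, an assumed 2 to 5 SAEs per 100 patient-years gives 18.9 × 0.02 = 0.4 to 28.4 × 0.05 = 1.4 SAEs among randomized patients in the whole window. That rate has no source in the documents. Only SAEs that a site misfiled would be affected, so the number at issue would be no larger than this.

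**The case against.** The strongest reply is that the protocol as a whole is clear. Table 6-1 and footnote 10 tell sites at the point of use to collect SAEs from consent. Section 6.1 speaks of non-serious adverse events in patients who were never treated, so the protocol itself does not apply the 7.1 window strictly. One hospitalization exception in 7.2.1 uses consent as its reference date. Entering an event as medical history also does not prevent a site from reporting it, and 7.2.2 is worded as an obligation while 7.1 is worded as advice. All of this stands and lowers the practical risk. It does not remove the conflict: 7.1 gives a general instruction with no exception, and a reader should not have to infer one from other sections.

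A second reply is timing. Enrollment closed on 6 July 2017, so new wording cannot affect any future screening. That also stands, and it makes a check of existing records the more useful part of the remedy.

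Three stronger readings are tempting but not supported.

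- A reader might infer that 7.5 exempts pregnancy-related SAEs, because it says: "Any SAE experienced during the pregnancy and unrelated to the pregnancy must be reported as an SAE". Section 3.6 makes that look serious: "Endogenous CGRP may play an important role in maintaining normal fetoplacental development, fetal survival, and vascular adaptation during pregnancy". But 7.5 is silent on related events and releases no one from 7.2.2, which applies regardless of causality. Section 7.2.1 lists congenital anomaly as a seriousness criterion, and 7.5 itself requires each pregnancy to be reported within 24 hours and followed for birth defects and complications. What remains is an ambiguity about whether the SAE form is also needed.
- A reader might infer that the medical-history instruction is ruled out by 6.2, which describes "relevant medical history/current medical condition present before signing informed consent". But 6.5.1 places clinically relevant examination findings present before randomization in medical history, the same cut-off as 7.1. The protocol is not uniform here, and the point does not depend on it.
- A reader might infer added risk in this window because exclusion criterion 5 makes patients stop preventive treatment. That criterion makes recent users ineligible. It instructs no one to stop, and the documents do not say how many patients did.

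**Conclusion.** The conflict between 7.1 and 7.2.2 is real and should be corrected. It is a wording inconsistency in which one sentence departs from the rest of the protocol and from the SAP. Its possible effect is that an SAE between consent and Visit 101 is held only as medical history, without a 24-hour report and without the flag the SAP uses.

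The exposed time is about 19 to 28 patient-years in randomized patients, a third to a half of the double-blind exposure. The number of affected events should be small, but the documents give no rate from which to derive it. It also depends on how many sites followed 7.1 rather than Table 6-1 and 7.2.2, which the documents cannot show. Any such event precedes study drug and lies outside the SAP's treatment-emergent definition. The efficacy comparison is not affected. The pregnancy wording in 7.5 merits a clarification only.

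**What to change.** 1. In protocol 7.1, limit the sentence on the Screening and Baseline Epochs to non-serious events, and add that SAEs from informed consent onward are reported under 7.2.2.
2. Because enrollment is closed, review medical-history entries dated between consent and Visit 101, including those of screen failures where recorded, against the seriousness criteria in 7.2.1. Any that qualify should be reported under 7.2.2 and entered on the AE page with the serious flag.
3. As a minor clarification, state in 7.5 that pregnancy-related SAEs are also reported under 7.2.2. This still matters for patients in open-label and post-trial access treatment.

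The cost is two short wording changes, a note to sites, one pass through a limited set of records, and possibly a few late SAE forms. No analysis method changes.
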